Cover Page

The effect of blood flow restriction training on rotator cuff strength in the healthy, untrained shoulder

Date: July 19, 2019

Pro00017362

NCT: 04530367

Status: Closed 12/7/2021

1) Protocol Title

The effect of blood flow restriction training on rotator cuff strength in the healthy, untrained shoulder

2) Investigator

[name]

3) Objectives

The aim of this study will be to determine the effect of upper extremity (UE) blood flow restriction (BFR) training for muscular strength improvement in individuals with no history of previous shoulder injury. The authors hypothesize that, participants who partake in BFR training will experience greater strength gains compared to a control group performing the same exercises.

4) Background

BFR training has been gaining popularity as a novel technique to develop greater strength and muscle mass in the rehabilitation setting. Many high-quality studies have examined the effects of muscle growth following controlled programs targeting strengthening at lower loads than typically used for hypertrophy. In rehabilitation, this provides the patient a significant advantage when muscular weakness and poor neuromuscular control predominate following an injury or surgery. If an individual is able to attain measurable improvements in muscle function utilizing low loads, then rehabilitation can be safer and more productive.

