What is currently unknown are the potential for improvements in strength of musculature proximal to the occluding cuff during BFR training. The rotator cuff serves as an excellent example due to its proximal location to typical UE placement as well as documented EMG specificity with certain exercises.^{4,5,15,16} Any strength gains, if elucidated with given program, should be easily detectable. Data from this study may possibly provide foundational information for future studies utilizing similar methods with different populations

The most frequently encountered side effects of BFR training is bruising and muscle soreness at the tourniquet site.^{12,25} BFR exercise does not show increase in markers for muscle damage such as myoglobin or creatine kinase.³ Deep vein thrombosis is infrequently seen at a rate of less than .1%.^{12,24}

5) Setting of the Human Research

The research will be conducted in an outpatient physical therapy clinic under close supervision of a trained and licensed physical therapist. Additional locations may include: Rice University Campus [name].

6) Resources available to conduct the Human Research

Equipment required for study will include: Delfi PTS Blood Flow Restriction Tourniquet System, MicroFET 2 hand-held dynamometer, cable column machine, free weights, VICON motion capture system.

7) Study Design

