Study participants will be randomly allocated in to 3 groups: control group (no exercise), exercise group, and BFR + exercise. Power analysis indicates the need for approximately 20 individuals in each group. Each exercise group will perform the same set of exercises 2 days/week for 8 weeks on their non-dominant upper extremity. Each group will also undergo strength testing at the same time throughout the protocol. Whereas the control group will only undergo testing in the same time periods. Muscle strength testing will be performed before the initiation of the program, at 4 weeks, and upon conclusion of the program. Testers will be blinded to group allocation. Muscle testing will be performed using manual hand-held dynamometry consistent with literature describing appropriate methods.^{9,18} Each manual muscle test will be performed as maximal exertion one repetition maximum test (1RM) three times to ensure most accurate dynamometry reading. For any baseball pitcher participants, motion capture measures will be taken before week 1 and after week 8. This will include sensors that measure range of motion and arm biomechanics for a maximum of 25 pitches in each session. To ensure test-retest reliability, each participant will undergo testing by the same individual. A familiarization protocol will be enforced to ensure all participants are familiar with testing measures and to decrease the amount of variability in intratester performance.

Exercises are as follows:

1. Cable column external rotation (at 90 degrees of abduction)
2. Cable column internal rotation (at 90 degrees of abduction)

3. Sidelying external rotation with weight (0 degrees)
4. Standing scaption with weight
 - These exercises have been found to incorporate the greatest electromyographic muscle activity of the rotator cuff in the literature.^{4,5,15,16}
 - The order of exercises will remain same for each participant in each group

BFR tourniquet placement will occur at the most proximal portion of the upper extremity. Tourniquet pressure will be applied at 50% of maximal limb occlusion pressure, to be re-measured each week. This is consistent with current literature recommendations for upper extremity BFR training.^{6,8,13}

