Resistances for each exercise will be determined by using 10-30% of 1RM (found during testing). This is consistent with current literature recommendations for upper extremity BFR training.^{6,8,13} Resistance may be increased as the subject tolerates so long as they stay within the 10-30% 1RM range. Following strength testing at 4 weeks, resistances may be adjusted due to strength gains.

a) Recruitment Methods

Potential study participants will be recruited from the local area who will be able to access clinic and equipment. Participants will be surveyed to ensure all inclusion and exclusion criteria are met.

b) Inclusion and Exclusion Criteria

Inclusion: participants must be healthy, untrained, volunteers who accept all provisions of the study and agree to complete the program in its entirety. Ages accepted will be 18-65.

Exclusion: potential participants will be excluded if:

1. Previous history of shoulder injury occurring in the laterality of choice
2. Current painful dysfunction resulting in exercise limitation
3. Any health-related exercise limitation as ordered by physician
4. Vascular compromise or previous vascular surgery
5. Ages outside of 18-65
6. Inability to access clinic and equipment
7. Currently involved in structured strength training regimen of the upper extremity

c) Study Endpoints

Exercise programs for each individual will terminate upon the completion of 16 sessions over 8 weeks. If any subject reports adverse effects (pain, injury, decreased range of motion), their program will be terminated and referral given for treatment by physician. Subject recruitment will occur over the course of 6-12 months or until reasonable power is achieved.

d) Procedures involved in the Human Research

Eligibility will be explained during the consent process with each participant. Minimal risk will be explained to the patient regarding exercise and blood-flow restriction training.

e) Data management

The PI will be responsible for all data collected, its confidential storage, and deletion after the study is completed.

f) Withdrawal of subjects

Subjects may withdraw at any time for any reason. Their data will be included if the individual has performed at least 4 weeks of the program. If the individual withdraws prior to 4 weeks, any pre-program testing will be deleted.

8) Risks to subjects

Minimal risks are present but may include arm pain due to tourniquet pressure or possible deep vein thrombosis.

9) Potential benefits to subjects

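### Section 7f drops randomised participants who withdraw before 4 weeks of training; if tourniquet pain makes this more common with BFR, the main comparison may be biased

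*Combined protocol and SAP*

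**What the plan says.** Section 7f (Withdrawal of subjects) sets two rules. For those who leave later, "Their data will be included if the individual has performed at least 4 weeks of the program". For those who leave earlier, "If the individual withdraws prior to 4 weeks, any pre-program testing will be deleted". The cut-off counts weeks of the program, so it is undefined for the no-exercise control group.

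Section 7c (Study Endpoints) has a separate stopping rule: "If any subject reports adverse effects (pain, injury, decreased range of motion), their program will be terminated". It gives no pain threshold. It does not say whether such a person is still tested or counts as withdrawn under 7f.

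On tolerability, section 4 (Background) says: "The most frequently encountered side effects of BFR training is bruising and muscle soreness at the tourniquet site". Section 8 says that risks "may include arm pain due to tourniquet pressure". Only the BFR group wears the tourniquet.

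The hypothesis in section 3 is that "participants who partake in BFR training will experience greater strength gains compared to a control group performing the same exercises". Section 7 plans about 20 people in each of three randomised groups, with strength tests at baseline, week 4 and the end of the 8-week program.

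The protocol states no analysis population, missing-data method or dropout allowance. Section 10 says only that data are coded by the group first allocated. That settles labels, not who is analysed.

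**The concern.** Whether a randomised person is analysed depends on what happens after training begins. In the comparison of interest, one arm has a source of discomfort that the other lacks. If people leave the BFR arm early more often, and for reasons linked to how much strength they would have gained, the remaining groups are no longer the groups that were randomised. The BFR versus exercise difference can then be wrong in either direction. Because the baseline is deleted, the analyst could not even compare those who left with those who stayed.

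Two gaps make the extent harder to judge. If a pain stop under 7c is treated as a withdrawal under 7f, reporting pain before week 4 leads directly to deletion. And those who leave or are stopped after week 4 keep their data, but nothing says they are tested at week 8.

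If leaving is unrelated to strength gain, there is no bias and only some precision is lost.

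**Working it through.** **The plan's own figure.** The figure of about 20 per group cannot be reproduced, because section 7 gives no effect size, SD, test, alpha, power or dropout. For scale, a two-sample t-test with 20 v 20, two-sided 0.05 and 80% power detects 0.909 SD.

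**Formula.** Let p be the share of an arm excluded before week 4. Let δ be the shortfall in mean gain, in SD, of those excluded relative to those who remain. The mean of the full randomised arm is the mean of those who remain minus p × δ, so analysing only those who remain overstates that arm by p × δ. Hence

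bias in BFR minus exercise = p_BFR × δ_BFR − p_ex × δ_ex.

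**Inputs.** The documents give no pain, stopping or withdrawal rate. All values of p and δ below are assumptions, and only exclusions before week 4 are counted.

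| Assumption | Calculation | Bias (SD) |
|---|---|---|
| Equal rates and equal shortfalls in both arms | difference cancels | 0 |
| Leaving unrelated to gain (δ = 0) | any p × 0 | 0 |
| 10% v 2.5% excluded, δ = 1.0 in both | (0.10 − 0.025) × 1.0 | +0.075 |
| 15% v 2.5% excluded, δ = 1.0 in both | (0.15 − 0.025) × 1.0 | +0.125 |
| 10% of BFR excluded, δ = 1.0 in BFR only | 0.10 × 1.0 | +0.10 |
| 15% of BFR excluded, δ = 1.0 in BFR only | 0.15 × 1.0 | +0.15 |
| 10% v 2.5% excluded, leavers would have gained 0.5 more | (0.10 − 0.025) × (−0.5) | −0.0375 |
| 15% v 2.5% excluded, leavers would have gained 0.5 more | (0.15 − 0.025) × (−0.5) | −0.0625 |

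A plus sign favours BFR.

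**Sensitivity to the rates.** With 5% excluded from the exercise arm and 20% from BFR, the bias is (0.20 − 0.05) × 0.5 = 0.075 to (0.20 − 0.05) × 1.0 = 0.15 SD for δ of 0.5 to 1.0. If there is truly no difference, the two-sided type I error is then 0.056 to 0.073 (normal approximation) instead of 0.05. With 30% excluded from BFR, the bias is 0.125 to 0.25 SD and the error 0.065 to 0.109.

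**Precision.** Losing 10% or 15% of 20 leaves 18 or 17 in the BFR arm. The detectable difference (same t-test settings) is:

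- 20 v 20: 0.909 SD
- 20 v 18: 0.935 SD
- 20 v 17: 0.951 SD

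The increase is about 3% (0.935/0.909) to 5% (0.951/0.909). An exclusion rate of 2.5% is half a person in 20, so no exercise participant is counted as lost here. Counting one gives 0.948 (19 v 18) and 0.963 (19 v 17). This loss may not arise if leavers are replaced, since section 7c says "Subject recruitment will occur over the course of 6-12 months or until reasonable power is achieved". Replacement would not remove a bias.

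**The case against.** The strongest case against has four parts.

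1. **Unequal withdrawal is not shown.** Section 7f concerns people who choose to leave, while 7c ends an exercise program and deletes nothing. Without the 7c link, the argument needs BFR participants to quit voluntarily before week 4 more often. The protocol calls the risks minimal, sets the tourniquet at half of limb occlusion pressure, uses light loads under a therapist's supervision, and enrols volunteers who have agreed to finish. This stands as a reason for caution: the 7c link is conditional and the differential is a possibility. It does not alter the 7f rule itself.

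2. **The size is chosen, not derived.** This is true. Even 0.15 SD is less than half of one standard error of the difference, √(2/20) = 0.316 SD, and the range crosses zero. That is why the point is an advisable change and not a fatal flaw.

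3. **The question may be about training, not assignment.** The hypothesis speaks of people who take part in BFR training. Someone who stops in week 2 may gain less simply because training stopped. That matters for the effect of assignment but is not necessarily a bias in the effect of training. The calculation does not separate the two. Selection of who stays could still distort the training effect, and an analysis of those trained for four weeks can be kept as secondary.

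4. **The remedy is partial.** Those who never return for testing add little. A mixed model assumes data are missing at random and does not correct absence that depends on unmeasured strength. This stands, and it is the reason for inviting people to testing as well as changing the analysis.

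**Conclusion.** The concern holds. Section 7f writes in an exclusion after randomisation, nothing else in the protocol undoes it, and the protocol names a source of pain found in only one arm of the key comparison.

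The size and direction of any bias cannot be derived from the documents. Under the main assumptions (10-15% v 2.5% excluded) it runs from an understatement of about 0.06 SD, through zero, to an overstatement of about 0.13 SD, or 0.15 SD if only the BFR leavers have a shortfall. Higher assumed rates give more. These figures measure departure from the effect of assignment and describe the whole problem, not the part that the change would remove. The change is worth making because it is cheap. Confidence is medium, because unequal early withdrawal is plausible but undocumented.

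**What to change.** Replace the four-week rule in 7f, and add the same text to 7c:

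> Ending or leaving the exercise program is not withdrawal from the study. All randomised participants who still consent are invited to the week-4 and week-8 strength tests, after physician clearance if they were stopped for pain or injury. Baseline and all later data collected are kept whatever the number of weeks trained, unless the participant asks for removal. The main analysis is by randomised group using all available data (for example, a mixed model for repeated measures with baseline, which assumes data are missing at random). Numbers and reasons for stopping, leaving and not being tested are reported by arm. An analysis of those with at least four weeks of training is secondary.

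Clearance is needed because section 7 specifies that "Each manual muscle test will be performed as maximal exertion one repetition maximum test (1RM) three times". The clinical pain threshold for stopping stays with the investigator. The wording also removes the difficulty of counting program weeks for the no-exercise group.

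The cost is protocol wording, the clearance step, and a few test visits that are already scheduled. Consent wording may need to change too, because the default moves from deletion to retention. The main estimate becomes the effect of assignment to BFR, which may be smaller than the effect in those who completed training.

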Subjects in either group may experience strength gains consistent with a strength-training program.

10) Provisions to protect the privacy interests of subjects

PHI information will not be used or published in the study as all information will be used to form aggregate data. The data will be kept on a secure password protected, hospital server and will be deleted after the study is complete. Subject data will be coded according to initial randomized group allocation.

11) Provisions to maintain the confidentiality of data

See #10

12) Cost to subjects

No costs will be incurred to the subjects.

13) Consent process

Participants will be educated on the data accrual process when they obtain the inclusion survey. Participation is completely voluntary and submission of declaration of inclusion is mandatory to be allocated to grouping and undergo testing/exercise program.

14) Process to document consent in writing

The standard consent form for this project will be explained and if the subject wishes to participate the consent will be signed prior to the start of the questionnaire.

RESOURCES:

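### Does coding the data by randomised group undermine the blinding of the strength testers?

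*Combined protocol and SAP*

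**What the plan says.** Three parts of the combined protocol and SAP bear on this.

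- **Blinding (section 7, Study Design).** "Testers will be blinded to group allocation". No mechanism is described. This is the only blinding that the plan mentions.
- **Outcome measurement (section 7).** "Muscle testing will be performed using manual hand-held dynamometry", and for test-retest reliability "each participant will undergo testing by the same individual". Tests take place before the programme, at 4 weeks and at the end. Training loads depend on the results: "Resistances for each exercise will be determined by using 10-30% of 1RM (found during testing"), and "Following strength testing at 4 weeks, resistances may be adjusted due to strength gains".
- **Data handling (section 10, privacy).** "Subject data will be coded according to initial randomized group allocation". The same section says that "The data will be kept on a secure password protected, hospital server" and that published results will be in aggregate form. Section 11 (confidentiality) only refers back to section 10, and section 7e makes the investigator responsible for the data and their storage.

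The documents do not say what the code looks like, whether it appears on strength-test records, who can open the server files, or whether participants also carry a study number unrelated to group.

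**The concern.** A code built from treatment arm is an awkward identifier in a trial that relies on blinded assessors. If every BFR participant carried the same visible label, a tester who learned its meaning once would know the arm of every BFR participant on that tester's list. A participant number without group information would reveal one person per disclosure.

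The outcome makes this worth asking. In hand-held dynamometry the tester takes part in the measurement, so expectation can influence the reading. Because a participant keeps the same tester throughout, knowledge gained before week 4 could affect both follow-up tests. Results also have to pass from testing to those setting the training loads while testing is still under way, and the plan does not name the identifier they travel under. What would be at stake is the comparison of strength gain between BFR and exercise alone, which is the study's hypothesis.

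**Working it through.** **1. Do the two sentences conflict?** Set side by side, section 7 restricts what testers may know, and section 10 says how data are classified.

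| Possible meaning of the section 10 code | Can section 7 still be met? |
|---|---|
| Data are classified for analysis by the arm first assigned | Yes; nothing need appear on a test record |
| An opaque group letter with the key held elsewhere | Yes, while the key stays away from testers |
| A readable group label in server files closed to testers | Yes |
| A readable group label on records that testers use | No; this use would itself breach section 7 |

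Only the last row does harm, and the documents do not describe it. The context favours the first row: the sentence stands in the privacy section beside aggregate reporting, and its reference to the initial allocation suits classification by the arm first assigned.

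**2. How far would one disclosure reach?** Section 7 refers to testers in the plural and gives each participant one tester. A tester who decodes a shared label therefore learns the arm only of the participants whom that tester sees. All of an arm would be exposed only if there were in fact a single tester, or if every tester of that arm learned the label.

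**3. What would a bias do if it occurred?** The plan has no figure to reproduce here. The only input from the documents is the arm size: "Power analysis indicates the need for approximately 20 individuals in each group". Everything else is assumed: a pairwise two-sided 5% t-test; a shift of *d* SD in the readings of each BFR participant whose arm the tester knows; *k* such participants out of 20; no shift in the comparator arm; and no true effect.

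- Degrees of freedom: 20 + 20 − 2 = 38; critical value 2.024.
- Noncentrality: (k/20) × d × √(20/2) = (k/20) × d × √10.
- Examples: k = 20, d = 0.3 gives 1 × 0.3 × 3.162 = 0.949; k = 10, d = 0.3 gives 0.474.

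False-positive rate from the noncentral t distribution:

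| BFR participants exposed | d = 0.1 | d = 0.2 | d = 0.3 |
|---|---|---|---|
| 20 of 20 | 6.1% | 9.5% | 15.2% |
| 10 of 20 | 5.3% | 6.1% | 7.5% |
| 5 of 20 | 5.1% | 5.3% | 5.6% |
| 3 of 20 | 5.0% | 5.1% | 5.2% |
| 1 of 20 | 5.0% | 5.0% | 5.0% |

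The exposure counts and shifts are chosen, not derived. The table says how much an assumed tester bias would matter; it says nothing about whether the coding rule produces one.

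**4. Would neutral numbers alter the result?** They would remove the code as a source of knowledge. They would not stop participants, who know whether they trained and whether they wore a cuff, from telling their tester. If 10 of 20 did so, the 10-of-20 row would apply under either coding scheme. The net gain from changing the code is therefore unknown.

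**The case for a change.** The best case for a change is that a safeguard should be written down and not inferred. Tester blinding is the plan's sole protection against assessment bias on an outcome that depends on the tester, and the document never says how it is achieved. The sentence directly follows the server-storage rule, so reading it as a rule for labelling records is natural. A password protects against outsiders, but testers may be insiders. A neutral number with a separately held list is cheap, and the fact that participants may talk does not justify leaving a second route open.

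Much of this stands. The silence is real, password protection alone does not settle who has access, and an unlinked study number is good practice. What does not stand is the step from silence to defect. Section 7 already sets the required result, and those running the trial cannot meet it while showing testers a readable arm label. A fuller rewrite, with a separate key-holder and a ban on joining the list until the last week 8 test, would go beyond what shielding testers requires. Staff delivering the exercise must in any case know who is in which training arm.

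**Conclusion.** The concern does not call for a change to the plan. The protocol leaves out an operational detail, but its blinding rule governs how that detail must be filled, and the coding sentence can be followed without breaching it. No statement in the documents shows that the blind is broken.

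No size can be attached to the point from the documents themselves. The illustrative rates, up to 15.2% in the most extreme case considered, require a readable shared label, sight of it by every tester of the BFR arm, and a 0.3 SD response to that knowledge. None of these is stated. With smaller exposures the assumed inflation quickly becomes slight: at 5 of 20 exposed it is at most 5.6%.

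This conclusion assumes that section 7 is applied as written, so that test records carry nothing that reveals the arm. If a tester was in fact shown a readable group code, that would be a departure from section 7 in conduct, and not a consequence of section 10.
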